APPENDIX IV

RTOG / EORTC Late Radiation Morbidity Scoring Scheme						
	0	1	2	3	4	5
SKIN	NONE	Slight atrophy; Pigmentation change; Some hair loss	Patch atrophy; Moderate telangiectasia; Total hair loss	Marked atrophy; Gross telangiectasia	Ulceration	
SUBCUTANEOUS TISSUE	NONE	Slight induration (fibrosis) and loss of subcutaneous fat	Moderate fibrosis but asymptomatic; Slight field contracture; <10% linear reduction	Severe induration and loss of subcutaneous tissue; Field contracture >10% linear measurement	Necrosis	D E A T H
MUCOUS MEMBRANE	NONE	Slight atrophy and dryness	Moderate atrophy and telangiectasia; Little mucous	Marked atrophy with complete dryness Severe telangiectasia	Ulceration	R E C T L Y
SALIVARY GLANDS	NONE	Slight dryness of mouth; Good response on stimulation	Moderate dryness of mouth; Poor response on stimulation	Complete dryness of mouth No response on stimulation	Fibrosis	R E L A T E D
SPINAL CORD	NONE	Mild L'Hermitte's syndrome	Severe L'Hermitte's syndrome	Objective neurological findings at or below cord level treated	Mono, para quadriplegia	T O R A D
BRAIN	NONE	Mild headache; Slight lethargy	Moderate headache Great lethargy	Severe headaches; Severe CNS dysfunction (partial loss of power or dyskinesia)	Seizures or paralysis Coma	

SYSTEM	GRADE	SYMPTOMS			ADDITIONAL INFORMATION
		GRADE 1	GRADE 2	GRADE 3	
EYE	NONE	Asymptomatic cataract Minor corneal ulceration or keratitis	Symptomatic cataract Moderate corneal Ulceration; Minor retinopathy or glaucoma	Severe keratitis; Severe retinopathy or detachment Severe glaucoma	Panophthalmitis/Blin dness
LARYNX	NONE	Hoarseness; Slight Arytenoid edema	Moderate arytenoid edema; Chondritis	Severe edema; Severe chondritis	Necrosis
LUNG	NONE	Asymptomatic or mild symptoms (dry cough) Slight radiographic appearances	Moderate symptomatic fibrosis or pneumonitis (severe cough) Low grade fever; Patchy radiographic appearances	Severe symptomatic fibrosis or pneumonitis Dense radiographic changes	Severe respiratory insufficiency/ Continuous o2/Assisted ventilation
HEART	NONE	Asymptomatic or mild symptoms; Transient T wave inversion & ST changes; Sinus tachycardia>110 (at rest)	Moderate angina on effort Mild pericarditis; Normal heart size; Persistent abnormal T wave and ST changes; Low ORS	Severe angina; Pericardial effusion; Constrictive pericarditis; Moderate heart failure; Cardiac enlargement; EKG abnormalities	Tamponade/Severe heart failure/Severe constrictive pericarditis
ESOPHAGUS	NONE	Mild fibrosis; Slight difficulty in swallowing solids; No pain on swallowing	Unable to take solid food normally; Swallowing semi-solid food; Dilatation may be indicated	Severe fibrosis; Able to swallow only liquids; May have pain swallowing Dilation required	Necrosis/Perforatio n Fistula

SMALL/LARGE INTESTINE	NONE	Mild diarrhea; Mild cramping; Bowel movement 5 times daily Slight rectal discharge or bleeding	Moderate diarrhea and colic; Bowel movement >5 times daily; Excessive rectal mucus or intermittent bleeding	Obstruction or bleeding, requiring surgery	Necrosis/Perforation Fistula	
LIVER	NONE	Mild lassitude; Nausea, dyspepsia; Slightly abnormal liver function	Moderate symptoms; Some abnormal liver function tests; Serum albumin normal	Disabling hepatic insufficiency; Liver function tests grossly abnormal; Low albumin; Edema or ascites	Necrosis /Hepatic coma or encephalopathy	
KIDNEY	NONE	Transient albuminuria; No hypertension; Mild impairment of renal function; Urea 25-35 mg%; Creatinine 1.5-2.0 mg%; Creatinine clearance>75%	Persistent moderate albuminuria (2+); Mild hypertension; No related anemia; Moderate impairment of renal function Urea>36-60mg% Creatinine clearance (50-74%)	Severe albuminuria; Severe hypertension Persistent anemia (<10g%); Severe renal failure; Urea >60 mg% Creatinine >4.0 mg% Creatinine clearance<50%	Malignant hypertension Uremic coma/Urea > 100%	
BLADDER	NONE	Slight epithelial atrophy Minor telangiectasia (microscopic hematuria)	Moderate frequency Generalized telangiectasia Intermittent macroscopic hematuria	Severe frequency & dysuria Severe generalized telangiectasia (Often with petechiae); Frequent hematuria; Reduction in bladder capacity (<150cc)	Necrosis/Contracted bladder (capacity <100cc) Severe hemorrhagic cystitis	

BONE	NONE	Asymptomatic; No growth retardation; Reduced bone density	Moderate pain or tenderness; Growth retardation; Irregular bone sclerosis	Severe pain or tenderness; Complete arrest of bone growth; Dense bone sclerosis	Necrosis/Spontaneous fracture	
JOINT	NONE	Mild joint stiffness; Slight limitation of movement	Moderate stiffness Intermittent or moderate joint pain; Moderate limitation of movement	Severe joint stiffness; Pain with severe limitation of movement	Necrosis/Complete fixation	

APPENDIX V

Harvard Cosmesis Scale	
Excellent	the treated breast looked essentially the same as the opposite breast.
Good	minimal but identifiable effects of radiation on the treated breast.
Fair	significant effects of radiation on the breast were noted.
Poor	severe normal tissue sequelae.

Appendix VI

Patient reported Breast Cancer Treatment Outcome Scale (Stanton AL, Krishnan L, Collins CA. Form or function? Part 1. Subjective cosmetic and functional correlates of quality of life in women treated with breast-conserving surgical procedures and radiotherapy. *Cancer*. 2001;91:2273–2281.)

We are interested in your evaluation of your physical appearance and functioning since your breast surgery and/or radiation.

Please rate the following items on this four-point scale, according to your evaluation at this time: 1) no difference between treated and untreated breast and area, 2) slight difference between treated and untreated breast and area, 3) moderate difference between treated and untreated breast and area, and 4) large difference between treated and untreated breast and area.

After rating all items, you are asked to place a check by any difference that was bothersome.

	1	2	3	4
Breast Size	No difference	Slight difference	Moderate difference	Large Difference
Breast texture/hardening	No difference	Slight difference	Moderate difference	Large Difference
Nipple appearance	No difference	Slight difference	Moderate difference	Large Difference
Breast Pain	No difference	Slight difference	Moderate difference	Large Difference
Breast Tenderness	No difference	Slight difference	Moderate difference	Large Difference
Breast Shape	No difference	Slight difference	Moderate difference	Large Difference
Breast Elevation (how high the breast is)	No difference	Slight difference	Moderate difference	Large Difference
Scar Tissue	No difference	Slight difference	Moderate difference	Large Difference
Fit of Bra	No difference	Slight difference	Moderate difference	Large Difference
Breast Sensitivity	No difference	Slight difference	Moderate difference	Large Difference
Fit of Clothing	No difference	Slight difference	Moderate difference	Large Difference

Appendix VII

CAVITY VISUALIZATION SCORE

0 = no visible seroma,

[figure not shown]
1 = scar/shadow

2 = seroma identifiable but with significant uncertainties

[figure not shown]
3 = seroma identifiable with minor uncertainties

4 = seroma easily identifiable, generally homogenous with slightly blurred margin

5 = seroma easily identifiable, homogenous with sharp boundaries.

Example of Well-defined Seroma Cavity, 4

Example of a poorly defined seroma cavity unsuitable for 3D CRT APBI, Score 1

APPENDIX VIII

CONTOURING GUIDELINES

1.0 Normal Structure And Target Contouring

The following structures will be contoured in all cases: the excision cavity throughout its respiratory motion (ITV), CTV, and planning target volume (PTV), the planning target for evaluation (PTV_EVAL), ipsilateral breast, contralateral breast, thyroid, ipsilateral and contralateral lung, and heart. Based on the 4D CT scan acquired during free breathing, the tumor bed will be segmented throughout its entire respiratory excursion to comprise the ITV. This will be expanded by 15 mm to comprise the CTV, although CTV will not include the pectoralis muscles, the chest wall, or within 5mm of skin. Questions about CTV are to be directed to [name]. The CTV must never be smaller than the ITV, and a Boolean operator may be necessary (Boolean CTV “OR” ITV). The PTV will be a 2 mm expansion of the CTV. Treatment planning will be performed on the average scan with heterogeneity corrections. The chin, shoulders and contralateral breast should be included in the scan. The target structures and normal tissue structures must be outlined on all CT slices. The average scan may be used for contouring structures other than the ITV.

In patients who have a very posterior or anterior cavity where the CTV is trimmed down to the ITV off of skin or pectoral muscle, the PTV should be expanded such that the ptv is a minimum 5 mm away from the ITV. This is intended to make sure that ptv to itv distance is a minimum of 5 mm (normally 17 mm after 15 mm expansion for ptv, but can be less in very posterior or very anterior cavities).

A. Thyroid

The thyroid is easily visible on a non-contrast CT due to its preferential absorption of Iodine, rendering it “brighter” or denser than the surrounding neck soft tissues. The left and right lobes of the thyroid are somewhat triangular in shape, and often do not converge anteriorly at mid-line. All “bright” thyroid tissue should be contoured.

B. Heart

The heart should be contoured beginning just below the level in which the pulmonary trunk branches into the left and right pulmonary arteries (PA). Above the PA, none of the heart's 4 chambers are present. All the mediastinal tissue below this level should be contoured, including the great vessels (ascending and descending aorta, inferior vena cava). The heart should be contoured on every contiguous slice thereafter to its inferior most extent near the diaphragm. If one can identify the esophagus, this structure should be excluded. Contouring along the pericardium itself, when visible, is appropriate, as the coronary arteries lie between the pericardium and the myocardium. The left anterior descending artery may be contoured, although no specific dose constraints are applied to this structure.

C. Whole Breast Reference Volume Contouring

Delineation of breast tissue extent remains difficult and free-handed CT interpretation by each individual investigator will yield significant variability. For the purposes of this protocol, the whole breast volume will be referred to as the whole breast reference volume and defined as all tissue volume, excluding lung, within the boundaries of standard whole breast tangential fields. The whole breast reference volume should also exclude any non-breast structure deep to the lung-rib interface such as heart, pre-cardiac fat, and liver.

An acceptable method of autocontouring with Eclipse is to convert the 50% isodose line from a standard tangential plan to a structure, then Boolean operator “breast” and “Body” (to include nipple which may be excluded). Subsequently, the Boolean operator can be used to remove any “breast” volume extending inside lung.

This is meant to be only an approximation of the actual breast tissue volume, and it is recognized some degree of adjacent soft tissue will be included. However, with this definition it is anticipated that this volume will be reproducible and consistent from case to case and that the process can be automated within the 3D planning system for time conservation.

To facilitate, the patient should be positioned in standard whole breast external beam treatment position. It is recommended that external marker wires be placed to indicate the clinical expectations of the external beam tangential field borders as a guide. The CT should be obtained from the mandible to the base of the lungs with a slice thickness of ≤ 5 mm.

Free-handed contouring of the breast

Free handed contouring will not be performed.

Automated contouring of the breast

Each 3D planning system has available different contouring functions and the specific methods may vary from system to system. Institutions are encouraged to investigate the capabilities of their planning system in regards to these contouring functions.

With the Eclipse planning system, standard tangent fields should be set up as in whole breast radiation therapy. Beam weighting should be optimized as is typically done for tangential field planning and normalized so that the 100% isodose line satisfactorily covers the volume of interest as determined by the set field geometries. A new Structure should be created titled “Breast Reference” and the “convert isodose line to structure” tool should be used to convert the 50% isodose line to the breast reference structure. This should then be booleaned with the “patient” or “external” structure to include the nipple. The lung and heart should be subtracted, and the structure should be reviewed and edited to insure that no tissue deep to the ribs is included (i.e. pericardial fat, liver, bowel).

Within the Pinnacle 3D planning system, auto-contouring the whole breast reference volume, as defined above, is easily accomplished and can be completed in several ways. Outlined below is an example of one of these methods: The Pinnacle 3D planning system has within its contouring functions a Region of Interest (ROI) expansion/contraction tool, found under Options within the contouring window, which allows a selected contour to be altered/limited automatically by selected ROIs already entered in the patient's plan. At the start of each case, the skin and lung contours will be entered with automated functions and the virtual standard whole breast tangent fields designed. By way of the ROI expansion/contraction tool, the planning system will start with the skin contour and alter it by limiting this contour to within the boundaries of the tangential fields and lung/chest wall interface, thus creating a new contour that represents the whole breast volume as defined above. Since this ROI expansion/contraction tool only uses entered contours, ROI's representing the borders of the tangential fields must first be entered. To represent the superior and inferior field borders, a simple box contour that encompasses the entire body on each CT slice superior and inferior to the tangential field borders, are entered under a new ROI (i.e., field borders). This can be accomplished by entering manually on each appropriate CT slice or expediting by utilizing the interpolation tools. Added to the newly created ROI, named here field borders, is a contour that is entered on every CT slice within the tangent fields that represents the posterior tangent border. This contour is placed along the posterior field border, extending the contour beyond the CT slice and viewing window. This contour can be entered manually on each appropriate CT slice or, to save time, the interpolation tool can be used to automate. Once field boundary contouring is complete, each CT slice will have either a simple encompassing box contour (if superior or inferior to the tangent fields) or a posterior field boundary contour (if within the tangential field borders). At this time, the ROI expansion/contraction window is brought up. Designate the skin as the source ROI and designate the lung and field borders limiting ROI's. Highlight "contract" as the function and designate the destination of the newly created ROI (simply create a new ROI which will then be listed in the destination list). Click on Proceed with Contraction to complete the process.

D. Target Contouring

Target definitions are listed here:

- ITV: THIS WILL REPRESENT THE PHYSIOLOGIC MOVEMENT OF THE TUMOR. The ITV will be representative of the tumor bed throughout its entire respiratory excursion.
- CTV – 1.5 cm beyond excision cavity. Volume expansion limited to **exclude pectoralis muscles, chest wall, and the first 5 mm beneath the skin** . This should not be smaller than the ITV.
- PTV: this will be a 2mm expansion of the CTV to account for intrafractional motion.
- PTV_EVAL – the PTV excluding pectoralis muscles, chest wall and the first 5 mm

beneath the skin.

Appendix IX

QUALITY ASSURANCE OF DOSE DISTRIBUTION

Each treatment plan shall be judged as:

• **Acceptable:**

- Dose volume histogram analysis of the target volume confirms 90% of the prescribed dose covers \geq 90% of the PTV_EVAL.
- Critical normal tissue DVHs within 5% specified value
- Maximum dose does not exceed 120% of prescribed dose.
- Dose delivered twice a day for a total of 10 treatments over a period of 5 to 10 days.

• **Unacceptable:**

- Dose volume histogram analysis of the target volume will confirm $<$ 90% of the prescribed dose covers $<$ 90% of the PTV_EVAL.
- Critical normal structure DVH exceeds 5% of the specified value
- Maximum dose exceeds 120% of prescribed dose.
- Dose delivered over a period of time extending greater than 10 days.

APPENDIX X

DOSIMETRY WORKSHEET:

Indices of an approved treatment plan

Patient Name			Case #		
Target	Organ/Target Volume (cc)	Dosimetry Index	Value	Unit	Ideal Value**
Seroma/Excision Cavity=ITV					
CTV					
PTV					
PTV-Eval		V90 (34.65 Gy)		%	>90%
Whole Breast Reference Volume (V50 and V100 are only required constraints to be met, all other are reporting only)		V5 (1.92 Gy)		%	<75% suggested
		V10 (3.85 Gy)		%	<70% suggested
		V25 (9.625Gy)		%	<55% suggested
		V50 (19.25 Gy)		%	< 45% IDEAL, <60% OK*
		V75 (28.875 Gy)		%	<30% suggested
		V100 (38.5 Gy)		%	< 23.5% IDEAL, <35% OK*
Contralateral Breast		D _{max}		cGy	<115 cGy

Ipsilateral Lung	V30 (11.55 Gy)	%	<15%
Contralateral Lung	V30 (11.55 Gy)	%	<15%
Heart (right sided)	V5 (1.92 Gy)	%	<5%
Heart (left sided)	V5 (1.92 Gy)	%	<40%
Thyroid	D _{max}	cGy	<115cGy

* plans which exceed the V50 >60% or V100>35% will be reviewed by [name] prior to approval. The definition and the method of collecting the above dosimetry quantities from an approved treatment plan for each patient are described as follows.

- Whole breast reference volume: Ideally, < 45% of the whole breast reference volume should receive $\geq 50\%$ of the prescribed dose and < 23.5% of the whole breast reference volume should receive the prescribed dose. As was done in NSABP B39, < 60% of the whole breast reference volume receiving $\geq 50\%$ of the prescribed dose and < 35% of the whole breast reference volume receiving the prescribed dose is acceptable, although not ideal.
- Contralateral breast: The contralateral breast reference volume, contoured using the same methods described for the ipsilateral breast reference volume, should receive <1.15 Gy (3% of prescribed dose) to any point.
- Ipsilateral lung: < 15% of the lung can receive 11.55 Gy (30% of the prescribed dose.)
- Contralateral lung: < 15% of the lung can receive 1.92 Gy (5% of the prescribed dose).
- Heart (right-sided lesions): < 5% of the heart should receive 1.92 Gy (5% of the prescribed dose).
- Heart (left-sided lesions): The volume of the heart receiving 1.92 Gy (5% of the prescribed dose) (V5) should be less than the 40%.
- Thyroid: maximum point dose of 1.15Gy (3% of the prescribed dose).

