inferior oblique (Rt PSIO) for a right breast lesion is described. First, 3 medial tangents (couch angle of 0° for 2 beams and 180° for 1 beam) and 1 lateral tangent (couch angle of 0°) are constructed. Typically, the medial tangents have a 10°-20° steeper gantry angle than whole breast tangents to spare more breast tissue. The lateral tangent may also have a slightly shallower gantry angle to spare breast tissue, provided that it does not exit through the contralateral breast. Next, couch angles are applied to each beam. Typical couch angles for the 3 anterior oblique fields are 35°-45° from a transverse plane. However, for the Rt AISO beam, particular care should be taken to ensure that the field exited superior to the heart. The couch angle used for the posterior oblique field is usually only 10°-20° to avoid entering through the ipsilateral arm, as well as collision problems with the gantry head and treatment couch. The 5-field technique is usually used for left-sided lesions and consists of Rt ASIO, Rt lateral, Rt AISO, Lt PSIO, and Lt PISO beams. The primary difference that makes this technique better suited for left-sided lesions is the elimination of the Lt AISO beam that would exit through the heart. The tradeoff is a larger volume of normal breast tissue irradiated. Each field typically has a universal 60° wedge in place for part of the treatment time. The heel of the wedge was directed anteriorly for all fields. The field edge is 5 mm beyond the PTV to account for penumbra. (Baglan KL, Sharpe SB, Jaffray D, et al. Accelerated partial breast irradiation using 3D conformal radiation therapy [3D-CRT]. *Int J Radiat Oncol Biol Phys.* 55:302-311, 2003.)

F. Dose Prescription and Delivery

- 4D-CRT will begin within 56 days of lumpectomy or re-excision of margins and within 6 weeks of study entry.
- A total of 38.5 Gy will be prescribed to the ICRU 50 reference point dose (usually isocenter). Two fractions per day, each of 3.85 Gy, separated by at least 6 hours, given on 5 treatment days (over a period of 5 to 10 days), will sum to 10 fractions and 38.5 Gy.

G. Dose Limitations for Normal Tissues

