- **Uninvolved normal breast:** Ideally, < 45% of the whole breast reference volume should receive $\geq 50\%$ of the prescribed dose and < 23.5% of the whole breast reference volume should receive the prescribed dose. However, a treatment plan will be considered acceptable if <60% of the whole breast reference volume receives $\geq 50\%$ of the prescribed dose and <35% of the whole breast reference volume receives the prescribed dose (as done in in NSABP B39). Plans which exceed these parameters ($V50 > 60\%$ or $V100 > 35\%$) must be evaluated by [name] prior to approval by the treating physician. For these calculations, the whole breast reference volume is defined as per Appendix VIII.
- **Contralateral breast:** The contralateral breast reference volume, contoured using the same methods described for the ipsilateral breast reference volume, should receive < 3% of the prescribed dose to any point.
- **Ipsilateral lung:** < 15% of the lung can receive 30% of the prescribed dose.

- **Contralateral lung:** < 15% of the lung can receive 5% of the prescribed dose.
- **Heart (right-sided lesions):** < 5% of the heart should receive 5% of the prescribed dose.
- **Heart (left-sided lesions):** The volume of the heart receiving 5% of the prescribed dose (V5) should be less than 40%.

Thyroid: maximum point dose of 3% of the prescribed dose.

H. Treatment Verification

Imaging dose for cone beam CT and kv imaging will be measured for the first 5 patients, and reported to the clinical PI.

- **Before first treatment**

- **For patients with fiducial markers placed:**

Portal images of each beam and a KV orthogonal pair (typically AP and lateral) must be obtained prior to initiation of treatment. Shifts will be made based on the KV orthogonal pair. Cone Beam CT matching and kilovoltage imaging should plan to align seroma cavity and clips rather than bony structures if there is a conflict. All shifts greater than 1 mm will be made. Any concerns about what structure is to be matched will be addressed to the supervising physician. Cone beam CT will be performed at the first fraction to ensure stable clip geometry and seroma volume, and may be performed at the discretion of the supervising physician.

- **For patients without fiducial markers placed:**

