7.0 Quality Assurance of Dose Distribution

DVHs for the PTV_EVAL, designated critical structures, and unspecified tissues will be submitted. Each treatment plan shall be judged as:

- **Acceptable:**

- Dose volume histogram analysis of the target volume confirms 90% of the prescribed dose covers \geq 90% of the PTV_EVAL.
- Critical normal tissue DVHs within 5% specified value.
- Maximum dose does not exceed 120% of prescribed dose.
- Dose delivered twice a day for a total of 10 treatments over a period of 5 to 10 days.

- **Unacceptable:**

- Dose volume histogram analysis of the target volume will confirm $<$ 90% of the prescribed dose covers $<$ 90% of the PTV_EVAL.
- Critical normal structure DVH exceeds 5% of the specified value
- Maximum dose exceeds 120% of prescribed dose.
- Dose delivered over a period of time extending greater than 10 days.

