Skin reaction(s) to radiation, including erythema, desquamation, etc. and any radiation complications or unusual or severe side effects of treatment will be recorded using RTOG acute and RTOG/ECOG late toxicity scoring. All toxicity from radiation is described in both acute and late terms, and this is often grouped together, because radiation delivery can lead to either side effect for normal tissue. Specifically, RTOG acute and RTOG/ECOG late radiation toxicity scoring parameters were originally described for breast conservation treatment, and will be used in this study.³³ Acute toxicity includes any side-effects during treatment or within three months following treatment and late toxicity includes side-effects from three months up to three years in this study (see Appendix III and IV). Both acute and late toxicity use scores from 0-5. Toxicity is not expected for other tissues but will be documented. Excess toxicity will be reported as detailed below (Section 14 and Section 15).

I. Copies of Dosimetry Calculations (see Appendix VI).

J. Patient Follow Up

Patient follow up will occur 4 weeks, 3 months, 6 months, 1 year, and three years post Radiation Therapy. Some patients will be followed beginning 4 weeks after treatment at L&M because it is closer to home for them. In these cases, [name] will be meeting with the patients.

- Vital status. If patient has expired, a data form must be submitted.
- Disease status, classified local, elsewhere, contralateral, regional, or distant. A local failure is defined as an ipsilateral breast tumor recurrence within the same quadrant of the breast as the original lumpectomy. An elsewhere failure is defined as an ipsilateral breast tumor recurrence not inside the same quadrant as the original lumpectomy. A contralateral breast cancer is defined as a breast cancer in the opposite breast. A regional failure is a recurrence in the axilla, internal mammary nodal chain, or supraclavicular lymph node basins. A distant failure is any metastasis to distant organs (i.e. bone, lung, liver, brain).
- Toxicity evaluation.
- Follow-up physical examination and mammographic results.

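### The Appendix X worksheet row for contralateral lung uses a dose level six times the one in Section 6.0 G and in the worksheet's own note

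*Combined protocol and SAP*

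**What the plan says.** Three places in the combined protocol and SAP state a contralateral lung index.

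- Section 6.0 G (dose limitations for normal tissues): "< 15% of the lung can receive 5% of the prescribed dose".
- Appendix X, worksheet row: "Contralateral Lung V30 (11.55 Gy) % <15" (a percentage limit).
- Appendix X, note under the worksheet: "Contralateral lung: < 15% of the lung can receive 1.92 Gy (5% of the prescribed dose".

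The notes under the worksheet are not offered as commentary. They are introduced with this sentence: "The definition and the method of collecting the above dosimetry quantities from an approved treatment plan for each patient are described as follows".

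Section 7.0 and Appendix IX then make plan acceptability depend in part on the normal-tissue limits: "Critical normal tissue DVHs within 5% specified value". Section 7.0 also requires the underlying curves: "DVHs for the PTV_EVAL, designated critical structures, and unspecified tissues will be submitted".

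**The concern.** The form defines a quantity that its own row does not request. A planner who follows the row enters the lung volume at 30% of dose; one who follows the note enters the volume at 5% of dose. Both values would sit in the same field, with nothing on the form to tell them apart.

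Two things are at stake. First, the acceptability rule needs one specified value for each structure. For contralateral lung the documents print two, so a verdict on this criterion could depend on which page the checker uses. Second, Endpoint C in Section 3.0 calls for treatment parameters to be collected and related to toxicity, and a field with two meanings cannot be pooled. Neither link is explicit: no section says that this worksheet feeds the Section 7.0 check or Endpoint C, so both are inferences.

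**Working it through.** **Inputs.** The prescribed dose is 38.5 Gy (Section 6.0 F). The index percentages and volume limits come from Section 6.0 G and Appendix X.

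**Step 1: reproduce the printed Gy values.**

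- 30% of dose: 0.30 × 38.5 = 11.55 Gy, as printed in the row.
- 5% of dose: 0.05 × 38.5 = 1.925 Gy, printed as 1.92 in the note.

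Each Gy figure agrees with its own percentage, so this is not an arithmetic slip. The ratio is 11.55 / 1.925 = 6.0, so it is not rounding either.

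**Step 2: compare all eight limits in Section 6.0 G with the worksheet table.**

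| Limit | Section 6.0 G | Worksheet table | Match |
|---|---|---|---|
| Breast V50 | 45% ideal, 60% acceptable | 45%, 60% | yes |
| Breast V100 | 23.5% ideal, 35% acceptable | 23.5%, 35% | yes |
| Contralateral breast, maximum | 3% = 115.5 cGy | 115 cGy | yes, to rounding |
| Ipsilateral lung, <15% at | 30% = 11.55 Gy | 11.55 Gy | yes |
| Contralateral lung, <15% at | 5% = 1.925 Gy | 11.55 Gy | **no** |
| Heart, right-sided, <5% at | 5% = 1.925 Gy | 1.92 Gy | yes |
| Heart, left-sided, <40% at | 5% = 1.925 Gy | 1.92 Gy | yes |
| Thyroid, maximum | 3% = 115.5 cGy | 115 cGy | yes, to rounding |

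Seven of eight match.

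**Step 3: logical relation of the two versions.** On a cumulative DVH the volume receiving at least 1.92 Gy cannot be smaller than the volume receiving at least 11.55 Gy, so V5 ≥ V30. A plan that fails the row therefore also fails the text limit. The reverse does not hold: any plan with V30 below 15% and V5 of 15% or more passes the row and fails the text.

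**Step 4: effect of the 5% tolerance.** The documents do not say whether the tolerance is relative or in percentage points.

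- Relative: 15 × 1.05 = 15.75%.
- Percentage points: 15 + 5 = 20%.

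On either reading, a plan with V30 below 15% and V5 above the bound (15.75% or 20%) still gets opposite verdicts.

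**Step 5: how many entries.** The documents give no lung DVH data and do not say how forms were completed. The number of affected entries lies between 0 and all patients, with the total given as 60 in Section 3.0 D and 70 in Section 13.0 C.

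**The case against.** The strongest reply is that the document largely settles the matter itself. Two prescriptive statements, Section 6.0 G and the note that is declared to define the worksheet quantities, agree with each other, and only one form cell differs. The worksheet is headed as a record of plans already approved, and its last column lists ideal values rather than limits. The specified value in the acceptability rule is then most naturally the one in Section 6.0 G. On this view the harm is one reporting field that may hold the wrong index. This has force and narrows the consequence, but it does not remove the conflict: a form completed as its row is printed still records a different and less demanding quantity than the stated limit.

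Other points can be weighed briefly.

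- **Dose to the opposite side is restricted anyway.** Section 6.0 D rejects plans with beams aimed at lung, heart or contralateral breast, and Section 6.0 G holds the contralateral breast below 3% of dose at any point. This makes discordant plans less likely. It does not show that V5 stays below 15%.
- **The worksheet says some indices are for reporting only.** That remark sits in the whole-breast cell and reads as applying to the breast indices. Even on a wider reading, a reporting field with two definitions is a data-capture fault.
- **The row could be an extraction artefact.** Agreement between the row's label and its Gy value does not alone exclude a cell repeated from the row above. But the row is complete, with organ, index, dose, unit and limit, and the neighbouring heart rows match their notes. An artefact is unlikely; a glance at the source PDF would settle it.
- **Severity.** The primary endpoint is untouched and the data are recoverable. Both are accepted, and they keep this from being a major point.

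**Conclusion.** The inconsistency is real. The contralateral lung row in Appendix X differs six-fold in dose level (11.55 against 1.925 Gy) from Section 6.0 G and from the note that defines the row, and it is the only one of eight limits to disagree. The error runs one way: the row can pass plans that the text fails, never the reverse, and the 5% tolerance does not close the gap.

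The conclusion that the documents conflict rests only on the printed text and the 38.5 Gy prescription, and assumes that the row was extracted faithfully. Its practical size is unknown. Effects on plan acceptance or on the toxicity correlations depend on the worksheet being used for those purposes, which the documents do not state. This should be corrected, but it does not threaten the primary result.

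**What to change.** Reconcile Section 6.0 G, the worksheet row and the worksheet note so that all three carry one contralateral lung index and one Gy value. Which index that should be is for the investigators to decide; no view is taken here.

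For patients already planned, read the reconciled index from the DVHs that Section 7.0 requires, so that the field holds one quantity for everyone.

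In the same edit, correct a separate but related cross-reference. Section 12.0 I reads "Copies of Dosimetry Calculations (see Appendix VI", but Appendix VI is the patient-reported outcome questionnaire; the reference should point to the intended dosimetry form.

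The cost is a small text edit, one cross-reference correction and a DVH look-up for each patient already planned. No new imaging or planning is needed.
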